5.1.4 Cohort F

The primary endpoint for the expansion part cohort F is disease control (DC).

Disease control (DC)

DC is defined as best overall response of complete response (CR) or partial response (PR) or confirmed stable disease (SD) (i.e. lasting till at least Week 24, 161 days taking into account allowable CTP window) where best overall response is defined according to RECIST version 1.1 from first treatment administration until the earliest of disease progression, death or last evaluable tumour assessment before start of subsequent anti-cancer therapy.

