The primary endpoint for expansion part is disease control (DC) defined as best overall response of complete response (CR) or partial response (PR) or confirmed stable disease (SD) (lasting for at least 24 weeks) or Non-CR/ Non-PD (lasting for at least 24 weeks) where best

overall response is defined according to RECIST version 1.1 from first treatment administration until the earliest of disease progression, death or last evaluable tumour assessment before start of subsequent anti-cancer therapy.

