7.3.1 Primary endpoint analyses

For dose finding cohorts A, B, C, and D (dose finding):

In order to identify the MTD, the number of patients with DLTs during the MTD evaluation period at each dose level will be presented. Patients who discontinue during the first treatment course for reasons other than DLT will be excluded from the determination of MTD.

For expansion cohort E:

Objective response will be analysed in terms of objective response rate, defined as the proportion of patients with best overall response of CR or PR (note that no confirmation is required for best overall response).

For cohorts D1 and D2:

PFS rate at 18th month will be derived using Kaplan Meier method. Cohort D1 for visceral vs. cohort D2 for non-visceral will be displayed separately. The details will be described in the TSAP.

For expansion cohort F

DC will be analysed in terms of DC rate, defined as the proportion of patients with best overall response of CR, PR, SD lasting for at least 24 weeks or non-CR/non-PD lasting for at least 24 weeks.

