7.3.2 Secondary endpoint analyses

For dose finding cohorts A, B, C, and D (dose finding):

There are no secondary endpoints.

For expansion cohorts E, F, D1 and D2:

The secondary endpoints will be analysed descriptively.

Disease control for Cohorts D1, D2 and E will be analysed in the same way as the primary analysis for Cohort F.

Time to objective response can only be calculated for patients with an objective response:

Time to objective response [days] = date of first documented CR or PR – date of first treatment administration +1.

Duration of objective response can only be calculated for patients with an objective response:

* For patients with disease progression or death:

Duration of objective response [days] = date of outcome – date of first assessment indicating objective response +1

* For patients without disease progression or death:

Duration of objective response (censored) [days] = date of outcome – date of first assessment indicating objective response +1

The censoring rules for duration of objective response (i.e. outcome and date of outcome) will be described in the TSAP. Only radiological assessments after first assessment indicating objective response should be taken into account.

Duration of disease control will be derived as follows:

* For patients with disease progression or death:

Duration of disease control [days] = date of outcome – date of first treatment administration +1

* For patients without disease progression or death:

Duration of disease control (censored) [days] = date of outcome – date of first treatment administration +1

The censoring rules for duration of disease control (i.e. outcome and date of outcome) will be described in the TSAP.

Progression-free survival will be derived as follows:

* For patients with “event” as an outcome for PFS:

PFS [days] = date of outcome – date of first treatment administration + 1

* For patients with “censored” as an outcome for PFS:

PFS (censored) [days] = date of outcome – date of first treatment administration + 1

Censoring rules for PFS will be described in the TSAP.

Objective response for Cohorts D1, D2 and F will be analysed in the same way as the primary analysis for Cohort E.

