Subsequent anti-cancer therapy started before progression or death, no more than one consecutively missed radiological assessments prior to start of subsequent anti-cancer therapy	Censored	Date of last radiological assessment before initiation of subsequent anti-cancer therapy

Only radiological assessments after first assessment indicating objective response will be taken into consideration.

Disease control (DC) (Cohorts E, D1 and D2 only)

For breast cancer, DC is defined as best overall response of CR or PR, or SD \geq Week 24 ($\geq=161$ days taking into account allowable CTP window), or Non-CR/Non-PD for \geq Week 24 ($\geq=161$ days taking into account allowable CTP window) where best overall response is defined according to RECIST version 1.1 from date of randomisation until the earliest of disease progression, death or last evaluable tumour assessment before start of subsequent anti-cancer therapy.

For NSCLC, DC is defined as best overall response of CR or PR, or SD ≥ 6 weeks, or Non-CR / Non-PD ≥ 6 weeks where best overall response is defined according to RECIST version 1.1 from date of randomisation until the earliest of disease progression, death or last evaluable tumour assessment before start of subsequent anti-cancer therapy.

Duration of DC

Duration of disease control is defined as the time from first treatment administration until the earliest of disease progression or death, among patients with disease control.

Duration of disease control will only be calculated for patients with a disease control. For patients with disease progression or death:

- Duration of disease control [days] = date of outcome – date of the first treatment administration + 1.

For patients without disease progression or death:

- Duration of disease control (censored) [days] = date of outcome – date of the first treatment administration + 1.

The censoring rules for duration of DC are given in [Table 5.2.2.2: 2](#).

Table 5.2.2.2: 2 Derivation rules for Duration of Disease Control

Situation	Outcome (event or censored)	Date of outcome
With baseline and post-baseline radiological assessments BUT no other anti-cancer therapy		
Alive and not progressed, no more than one consecutively missed radiological assessments	Censored	Date of last radiological assessment
Alive and not progressed, two or more consecutively missed radiological assessments	Censored	Date of last radiological assessment prior to missed radiological assessments

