7.4.4 Cohort F

Disease control (DC)

DC as assessed by investigators is defined as a best overall response of CR or PR or SD and will be analysed. Descriptive statistics including number of treated patients, number of patients with objective response as best overall response and the corresponding percentages will be presented and evaluated.

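### SAP 5.1.4 and 7.4.4 leave durable Non-CR/Non-PD out of cohort F's primary endpoint, and 7.4.4 counts objective responders instead of disease control

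*SAP*

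**What the plan says.** Protocol 5.1.1 defines DC in cohort F as CR, PR, stable disease of at least 24 weeks, "or Non-CR/ Non-PD (lasting for at least 24 weeks"). Protocol 7.3.1 repeats this for the analysis: "SD lasting for at least 24 weeks or non-CR/non-PD lasting for at least 24 weeks".

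SAP 5.1.4 gives a shorter list: "DC is defined as best overall response of complete response (CR) or partial response (PR) or confirmed stable disease (SD"), with stable disease required to last to Week 24 (161 days, allowing for the visit window). Non-CR/Non-PD is not mentioned.

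SAP 7.4.4, the analysis section, reads: "DC as assessed by investigators is defined as a best overall response of CR or PR or SD and will be analysed". It gives no duration and no cross-reference to 5.1.4. The statistic to be tabulated is the "number of patients with objective response as best overall response and the corresponding percentages will be presented and evaluated".

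SAP 5.2.2.2 does include Non-CR/Non-PD from Week 24 for breast cancer, but under the heading "Disease control (DC) (Cohorts E, D1 and D2 only"), which leaves cohort F out. SAP 4.2 declares no changes from the protocol.

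**The concern.** Non-CR/Non-PD is how disease that is neither resolved nor progressing is recorded in patients without measurable lesions. If the rule omits it, an eligible bone-only patient who is stable for 24 weeks is a success under the protocol and a failure under the SAP. The error affects a primary endpoint in a cohort of 20, where each misclassified patient moves the rate by 1/20 = 5 percentage points, against the 60% that protocol 7.7 calls clinically relevant.

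It also carries into a secondary endpoint: "Duration of disease control will only be calculated for patients with a disease control". The same patients therefore drop out of duration of DC.

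SAP 7.4.4 has two further faults. Its definition admits stable disease of any qualifying length, which would raise the rate. Its count is objective responders, which is a secondary endpoint for cohort F and would lower the rate. A programmer working from 7.4.4 alone could produce a number that is neither the protocol's endpoint nor that of 5.1.4.

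**Working it through.** **Step 1: the definitions side by side.**

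| Source | CR, PR | SD | Non-CR/Non-PD |
|---|---|---|---|
| Protocol 5.1.1 and 7.3.1, cohort F | yes | at least 24 weeks | at least 24 weeks |
| Protocol synopsis, cohort F | yes | at least 24 weeks | not listed |
| SAP 5.1.4, cohort F | yes | to Week 24 (161 days) | not listed |
| SAP 7.4.4, cohort F, definition | yes | no duration | not listed |
| SAP 7.4.4, cohort F, count | yes | no | no |
| SAP 5.2.2.2, breast cancer (heading: E, D1, D2) | yes | at least 161 days | at least 161 days |

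Protocol 3.2 adds a further version by still naming OR rate as the primary endpoint of cohort F.

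**Step 2: who is affected.** Protocol 3.3.2 (criterion 10 for D1, D2 and F) admits measurable disease or non-measurable bone-only disease. SAP 5.1.2 makes PR and SD available only with measurable disease at baseline, and Non-CR/Non-PD only with non-measurable disease. Protocol Appendix 10.4 agrees: without measurable disease, the possible time-point responses are CR, Non-CR/Non-PD, NE and PD. Under SAP 5.1.4 a bone-only patient can therefore count only with a CR. For patients with measurable disease, 5.1.4 matches the protocol apart from the stated visit window.

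**Step 3: reproduce the plan's figures (protocol 7.7, n = 20, exact binomial).**
- P(X ≥ 10 | 0.60) = 0.8725; stated 87%.
- P(X ≥ 10 | 0.80) = 0.9994; stated above 99%.
- P(X ≥ 8 | 0.20) = 0.0321; stated 3%.

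**Step 4: effect of the omission.** Let b be the bone-only share and c the CR rate among bone-only patients. Neither is in the documents, so both are assumptions. Also assume the true DC rate under the protocol definition is 60% in measurable and bone-only patients alike. Then

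countable rate = 0.60 × (1 − b) + c × b.

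For example, b = 0.30 and c = 0 gives 0.60 × 0.70 = 0.42, or 20 × 0.42 = 8.4 expected events instead of 12. Each cell shows the countable rate, then P(X ≥ 10 of 20).

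| b | c = 0 | c = 0.05 | c = 0.10 |
|---|---|---|---|
| 0 | 60%, 0.87 | 60%, 0.87 | 60%, 0.87 |
| 20% | 48%, 0.52 | 49%, 0.55 | 50%, 0.59 |
| 30% | 42%, 0.31 | 43.5%, 0.36 | 45%, 0.41 |
| 50% | 30%, 0.05 | 32.5%, 0.08 | 35%, 0.12 |

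**Step 5: effect of the 7.4.4 count.** If objective responders were tabulated, P(X ≥ 10 of 20) would be 0.003, 0.05 or 0.24 at assumed OR rates of 20%, 30% or 40%.

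**The case against.** The strongest reply is that the intent can be recovered. SAP section 3 says the document is based on the protocol's planned analysis, and 4.2 declares no change, so protocol 7.3.1 could be read as governing. SAP 5.1.2 already derives a Week 24 Non-CR/Non-PD category for breast cancer. Cohort E requires measurable disease, so that category can serve only the breast cohorts. The count sentence in 7.4.4 repeats the sentence used for OR in SAP 7.4.2 and 7.5.2.2 and looks like a copying slip. Table shells and a technical SAP exist that may already be right. All of this makes a drafting error likely, but it does not correct a stated primary-endpoint rule that gives a different count from the protocol.

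A second reply is that the protocol is not uniform. Its section 5.1.2 defines DC for D1, D2 and E without Non-CR/Non-PD, although D1 and D2 admit the same bone-only patients. That is true, and it weakens any argument for a single definition drawn from protocol 7.3.2 ("Disease control for Cohorts D1, D2 and E will be analysed in the same way as the primary analysis for Cohort F"), since that sentence concerns the analysis. It does not touch cohort F, for which the endpoint and analysis sections agree with each other.

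A third reply is that the figures rest on assumptions, the cohort is descriptive, and 10 of 20 is not a decision rule. This stands as a limit on the size of the bias. It does not alter the definitional error or its direction.

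**Conclusion.** The concern holds. SAP 5.1.4 misstates cohort F's primary endpoint by omitting Non-CR/Non-PD of at least 24 weeks. SAP 7.4.4 repeats the omission, drops the 24-week rule and names a different endpoint as the count. These are certain from the text and should be corrected before the cohort F result is produced.

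The direction of the 5.1.4 error is also certain: it can only lower the DC rate. Its size is not known. It is zero if no bone-only patient has durable Non-CR/Non-PD as best response, and grows with the bone-only share. On the assumptions shown (60% DC in both subgroups, 20% to 50% bone-only, 0 to 10% CR among them), the countable rate falls to between 50% and 30%, and the planning probability of 0.87 to between 0.59 and 0.05. The sample-size figures in protocol 7.7 are themselves correct and do not change after the fix.

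**What to change.** - **SAP 5.1.4:** define DC for cohort F as CR, PR, SD to at least Week 24 (161 days or more), or Non-CR/Non-PD to at least Week 24 (161 days or more), as 5.2.2.2 already does for breast cancer.
- **SAP 7.4.4:** replace the restated definition with a reference to 5.1.4, and count patients with disease control instead of objective response. Check the matching table shell.
- **Protocol:** add Non-CR/Non-PD to the cohort F line of the synopsis, and name DC instead of OR for cohort F in section 3.2. Section 5.1.2 and the synopsis line on secondary DC should be aligned for D1 and D2 at the same time.

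The SAP changes alone repair the primary endpoint. They cost wording in two sections and, if needed, one table shell; SAP 5.1.2 already derives the category, so no new data are required. The protocol edits are short, but protocol 8.1 requires ethics committee and authority approval for changes made by amendment, so they can wait for the next amendment.

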5.2 SECONDARY ENDPOINTS

5.2.1 Key secondary endpoints

Not applicable.

5.2.2 Other secondary endpoints

5.2.2.1 Cohorts A, B, C, and D

There are no secondary endpoints.

5.2.2.2 Cohorts E, F, D1 and D2

Time to OR

Proprietary confidential information © 2021 Boehringer Ingelheim International GmbH or one or more of its affiliated companies

Time to objective response is defined as the time from first treatment administration until first documented CR or PR.

Time to objective response will only be calculated for patients with an objective response:

- Time to OR [days] = date of first documented CR or PR - date of first treatment administration +1

Duration of OR

Duration of objective response is defined as the time from first documented CR or PR until the earliest of disease progression or death among patients with objective response.

Duration of objective response will only be calculated for patients with an objective response. For patients with disease progression or death:

- Duration of objective response [days] = date of outcome – date of first assessment indicating OR + 1.

For patients without disease progression or death:

- Duration of objective response (censored) [days] = date of outcome – date of first assessment indicating objective response + 1

The censoring rules for duration of OR are given in [Table 5.2.2.2: 1](#).

Table 5.2.2.2: 1 Derivation rules for Duration of Objective Response

Situation	Outcome (event or censored)	Date of outcome
No other anti-cancer therapy		
Alive and not progressed, no more than one consecutively missed radiological assessments	Censored	Date of last radiological assessment
Alive and not progressed, two or more consecutively missed radiological assessments	Censored	Date of last radiological assessment prior to missed radiological assessments
Progressed, zero or one missed radiological assessment prior to progression	Event	Date of radiological assessment of progression
Progressed, but two or more consecutively missed radiological assessments prior to progression	Censored	Date of last radiological assessment prior to missed assessments
Death but no progression, zero or one missed radiological assessment prior to death	Event	Date of death

Proprietary confidential information © 2021 Boehringer Ingelheim International GmbH or one or more of its affiliated companies

Situation	Outcome (event or censored)	Date of outcome
Death without progression, but two or more consecutively missed radiological assessments prior to death	Censored	Date of last radiological assessment prior to missed assessments
Initiation of subsequent anti-cancer therapy		
Subsequent anti-cancer therapy started before progression or death, no more than one consecutively missed radiological assessments prior to start of subsequent anti-cancer therapy	Censored	Date of last radiological assessment before initiation of subsequent anti-cancer therapy

Only radiological assessments after first assessment indicating objective response will be taken into consideration.

Disease control (DC) (Cohorts E, D1 and D2 only)

For breast cancer, DC is defined as best overall response of CR or PR, or SD \geq Week 24 ($\geq=161$ days taking into account allowable CTP window), or Non-CR/Non-PD for \geq Week 24 ($\geq=161$ days taking into account allowable CTP window) where best overall response is defined according to RECIST version 1.1 from date of randomisation until the earliest of disease progression, death or last evaluable tumour assessment before start of subsequent anti-cancer therapy.

For NSCLC, DC is defined as best overall response of CR or PR, or SD ≥ 6 weeks, or Non-CR / Non-PD ≥ 6 weeks where best overall response is defined according to RECIST version 1.1 from date of randomisation until the earliest of disease progression, death or last evaluable tumour assessment before start of subsequent anti-cancer therapy.

Duration of DC

Duration of disease control is defined as the time from first treatment administration until the earliest of disease progression or death, among patients with disease control.

Duration of disease control will only be calculated for patients with a disease control. For patients with disease progression or death:

- Duration of disease control [days] = date of outcome – date of the first treatment administration + 1.

For patients without disease progression or death:

- Duration of disease control (censored) [days] = date of outcome – date of the first treatment administration + 1.

The censoring rules for duration of DC are given in [Table 5.2.2.2: 2](#).

Table 5.2.2.2: 2 Derivation rules for Duration of Disease Control

Situation	Outcome (event or censored)	Date of outcome
With baseline and post-baseline radiological assessments BUT no other anti-cancer therapy		
Alive and not progressed, no more than one consecutively missed radiological assessments	Censored	Date of last radiological assessment
Alive and not progressed, two or more consecutively missed radiological assessments	Censored	Date of last radiological assessment prior to missed radiological assessments
Progressed, zero or one missed radiological assessment prior to progression	Event	Date of radiological assessment of progression
Progressed, but two or more consecutively missed radiological assessments prior to progression	Censored	Date of last radiological assessment prior to missed assessments
Death but no progression, zero or one missed radiological assessment prior to death	Event	Date of death
Death without progression, but two or more consecutively missed radiological assessments prior to death	Censored	Date of last radiological assessment prior to missed assessments
Initiation of subsequent anti-cancer therapy		
Subsequent anti-cancer therapy started before progression or death	Censored	Date of last radiological assessment before subsequent anti-cancer therapy
No baseline and/or post-baseline imaging and subsequent anti-cancer therapy started prior to a death	Censored	Date of randomisation (or first treatment administration, in non-randomised trials)

[figure not shown]
Progression-free survival (PFS)The derivation of endpoint PFS refers to [Section 5.1.3](#).Last evaluable imaging

Proprietary confidential information © 2021 Boehringer Ingelheim International GmbH or one or more of its affiliated companies

[figure not shown]
An evaluable radiological image for the censoring of PFS is an image for which an overall response assessment of SD, Non-CR/Non-PD, PR or CR has been assigned. This is used for censoring of patients without progression at end of trial, or censoring prior to missed assessments, or censoring prior to subsequent anti-cancer therapy

Objective response (OR) (Cohorts F, D1 and D2 only)

[figure not shown]
The definition for OR is the same as the primary endpoint for cohort E , refer to [Section 5.1.2.](#)

[figure not shown]
Proprietary confidential information © 2021 Boehringer Ingelheim International GmbH or one or more of its affiliated companies

[figure not shown]
Proprietary confidential information © 2021 Boehringer Ingelheim International GmbH or one or more of its affiliated companies

[figure not shown]
Proprietary confidential information © 2021 Boehringer Ingelheim International GmbH or one or more of its affiliated companies

Proprietary confidential information © 2021 Boehringer Ingelheim International GmbH or one or more of its affiliated companies

Proprietary confidential information © 2021 Boehringer Ingelheim International GmbH or one or more of its affiliated companies

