
Secondary endpoints:
 
For each dose finding cohorts A, B, C and D:
 
* No secondary endpoint 
For each expansion cohorts E, F, D1 and D2:
 
* Disease control (CR, PR, SD lasting at least 24 weeks per RECIST 1.1) (only for Cohorts D1, D2 and E)* Time to objective response* Duration of objective response* Duration of disease control* Progression-free survival (PFS)* Objective response (only for Cohorts D1, D2 and F)		
Safety criteria:	Incidence and severity of reported AEs. AEs will be assessed using the National Cancer Institute [NCI] Common Terminology Criteria for Adverse Events [CTCAE] version 4.03 (R10-4848)	

Name of company:		Boehringer Ingelheim	
Name of finished product:		Not applicable	
Name of active ingredient:		Xentuzumab (BI 836845)	
Protocol date: 30 Nov 2016	Trial number: 1280.18		Revision date: 04 Mar 2022
Statistical methods:		All endpoints for each dose finding cohorts and each expansion cohorts will be analysed using descriptive statistics. For dose finding cohorts, inter-patient dose (de-)escalation is guided by a Bayesian Logistic Regression Model (BLRM) with overdose control that will be fitted to binary toxicity outcomes. The estimate of parameters will be updated as data are accumulated using the BLM. At the end of each dose finding, the toxicity probability at each dose level will be calculated to determine an estimate of the MTD.	

FLOW CHART – COHORT A (SOLID TUMOURS)

Study period	Screening (a)	Treatment Courses (b)								EOTV (c)	FU (d)
		Course 1				Course 2 onwards					
Visits (V)	Screening	1	2	3	4	1	2	3	4		
Days	Within 28d before C1V1	1	8 ±1	15 ±1	22 ±1	1 ±2	8 ±2	15 ±2	22 ±2	Within 7d after last drug intake	42 +7d after last drug intake
Informed consent (1)	X										
Demographics	X										
Medical history	X										
Inclusion/exclusion criteria (2)	X (2)	X (2)									
Physical exam (3)	X	X				X				X	X
Height	X										
Body weight	X	X				X				X	X
Vital signs (4)	X	X	X	X	X	X				X	X
ECOG performance status	X	X				X				X	X
12-lead ECG (triplicate) (5)	X	X		X		X		X		X	X
Safety lab (6)	X	X	X	X	X	X		X (7)		X	X
Archival tumour tissue collection (8)	X										
Blood sample for biomarkers (9)	X	X	X			X				X	X
Pharmacokinetics (10)		X	X			X				X	X
Pharmacogenomics and cfDNA (11)		X				X (12)				X	
PGx Plasma -exosomal RNA (13)		X		X		X				X	
DNA banking (14)		X									
Immunogenicity (ADA) (15)		X	X			X				X	X

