5.1.2 Secondary Endpoint(s)

[figure not shown]
For dose finding cohorts A, B, C, and D (dose finding)

[figure not shown]
There are no secondary endpoints.

[figure not shown]
For expansion cohorts E, F, D1 and D2:

The secondary endpoints are:

- * Cohorts D1, D2 and E only: Disease control (DC) defined as best overall response of complete response (CR) or partial response (PR) or confirmed stable disease (SD) (lasting for at least 24 weeks) where best overall response is defined according to RECIST version 1.1 from first treatment administration until the earliest of disease progression, death or last evaluable tumour assessment before start of subsequent anti-cancer therapy.
- * Time to objective response defined as the time from first treatment administration until first documented complete response (CR) or partial response (PR).
- * Duration of objective response defined as the time from first documented complete response (CR) or partial response (PR) until the earliest of disease progression or death among patients with objective response.
- * Duration of disease control defined as the time from first treatment administration until the earliest of disease progression or death, among patients with disease control.
- * Progression-free survival (PFS) defined as the time from first treatment administration until tumour progression according to RECIST 1.1 or death from any cause, whichever occurs earlier.
- * Cohorts D1, D2 and F only: Objective response (OR) defined as best overall response of complete response (CR) or partial response (PR), where best overall response is determined according to Response Evaluation Criteria In Solid Tumours (RECIST) version 1.1 from date of first treatment administration until the earliest of disease progression, death or last evaluable tumour assessment before start of subsequent anti-cancer therapy.

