4.2 CHANGES

Not applicable.

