5.1.2 Cohort E

The primary endpoint for the expansion part cohort E is objective response (OR).

Objective response (OR)

OR is defined as best overall response of complete response (CR) or partial response (PR), where best overall response is determined according to Response Evaluation Criteria In Solid Tumours (RECIST) version 1.1 from date of first treatment administration until the earliest of disease progression, death or last evaluable tumour assessment before start of subsequent anti-cancer therapy.

Best overall response

An adequate RECIST tumour assessment includes an assessment of target lesions (only for patients with measurable disease at baseline), as well as radiological tests to evaluate non-target lesions if any and to search for new lesions. In case no RECIST tumour evaluation has been performed, the assessment will be set to missing.

Best overall response is calculated based on the “overall” visit response from each assessment. Best overall response represents the best response a patient has had during his/her time in the study until progression, last evaluable assessment in the absence of progression or the start of subsequent anti-cancer therapy. For patients whose progression event is death, best overall response will be calculated based on data until the last evaluable RECIST assessment prior to death. (note that no confirmation is required for best overall response)

The following categories of best overall response will be derived:

- Complete response (CR)
- Partial response (PR) – possible only for patients with measurable disease at baseline
- Stable disease (SD) – possible only for patients with measurable disease at baseline

Proprietary confidential information © 2021 Boehringer Ingelheim International GmbH or one or more of its affiliated companies

- Subcategory “SD \geq Week 24” for breast cancer and “SD \geq 6 weeks” for NSCLC: calculated from randomization/treatment start until the earliest of disease progression, death or last evaluable tumour assessment before start of subsequent anti-cancer therapy. Here SD \geq Week 24 includes SD \geq 161 days taking into account allowable CTP window.
- Non-CR/Non-PD – possible only for patients with non-measurable disease at baseline

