7.5.2.2 Cohorts E and F, D1 and D2

Disease control (Cohorts E, D1 and D2 only)

Disease control (DC) is defined as best overall response of complete response (CR) or partial response (PR) or stable disease (SD) (defined in [Section 5.2.2.2](#)). Only descriptive statistics are planned for this section of the report.

Time to OR

For patients with objective response, time to objective response will be shown on patient level. A set of summary statistics for time to objective response on cohort level will also be produced.

Duration of OR

KM estimates will be calculated for each treatment group to provide estimates of the median, 25th and 75th percentiles and their corresponding 95% CIs.

Duration of DC

Duration of DC will be analysed similarly to Duration of OR, see above.

Progression free survival

[figure not shown]
Kaplan-Meier estimates and 95% CIs (based on Greenwood's method) will be calculated. Furthermore progression free survival times on patient level will be shown and if applicable descriptive statistics including, but not limited to, the lower quartile (P25), Median and the upper quartile (P75) will be computed.

Objective response (Cohorts F, D1 and D2 only)

[figure not shown]
OR as assessed by investigators is defined as a best overall response of CR or PR and will be analysed. Descriptive statistics including number of treated patients, number of patients with

Proprietary confidential information © 2021 Boehringer Ingelheim International GmbH or one or more of its affiliated companies

objective response as best overall response and the corresponding percentages will be presented and evaluated.

Proprietary confidential information © 2021 Boehringer Ingelheim International GmbH or one or more of its affiliated companies

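### Cohort E disease control: the SAP counts stable disease of 6 weeks where the protocol requires 24, and declares no change

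*SAP*

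**What the plan says.** **Protocol.** Three places set the rule for cohort E, and all lead to 24 weeks.

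- The synopsis lists DC as a secondary endpoint with "SD lasting at least 24 weeks per RECIST 1.1) (only for Cohorts D1, D2 and E".
- Section 5.1.2 defines it for D1, D2 and E as CR, PR "or confirmed stable disease (SD) (lasting for at least 24 weeks", counted from first treatment.
- Section 7.3.2 states: "Disease control for Cohorts D1, D2 and E will be analysed in the same way as the primary analysis for Cohort F". Section 7.3.1 sets the cohort F rule at 24 weeks, for SD and for Non-CR/Non-PD.

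**SAP.** Section 5.2.2.2 splits the definition by tumour type. Breast cancer keeps Week 24, written as at least 161 days. The NSCLC sentence begins "For NSCLC, DC is defined as best overall response of CR or PR, or SD" and sets the limit at "6 weeks where best overall response is defined according to RECIST version 1.1 from date of randomisation". The best-overall-response categories in SAP 5.1.2 carry the same 6-week NSCLC subcategory, with duration "calculated from randomization/treatment start until the earliest of disease progression, death or last evaluable tumour assessment before start of subsequent anti-cancer therapy". SAP 7.5.2.2 takes its analysis definition from there: "Disease control (DC) is defined as best overall response of complete response (CR) or partial response (PR) or stable disease (SD) (defined in" Section 5.2.2.2).

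**Declared changes.** SAP 4.1 lists only COVID-19 summaries, SAP 4.2 reads "Not applicable", and SAP 4.3 does not mention DC.

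**The concern.** The SAP presents itself as an elaboration of the protocol's analysis, yet it replaces the duration requirement of a named protocol endpoint without saying so. SAP 5.1.2 also disagrees with itself: the same section closes by giving 24 weeks as the minimum required duration of SD.

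The new limit also does no work. A 6-week requirement that falls before the first scheduled scan turns durable control into absence of progression at the first scan. A patient with SD at Week 8 and progression at Week 16 counts as controlled under the SAP and not under the protocol. Because duration of DC is calculated only among patients with DC, that patient enters the duration analysis too. In a single-arm cohort of 20 with no test, the descriptive rates are the result, so their definitions have to be the stated ones.

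**Working it through.** **Reproducing the plan's own figures.** The SAP's Week 24 limit is 24 × 7 − 7 = 161 days, as stated. The Week 8 scan window is 56 ± 7 = 49 to 63 days, as in footnote 18 of the cohort E flow chart.

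**Where the scans fall.** Scans are timed from xentuzumab. The response clock starts at first treatment including the 9-day run-in (protocol 5.1.1, SAP 4.3), so 9 days are added:

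| Scan | Days from xentuzumab | Days from first treatment |
|---|---|---|
| Week 8 | 49–63 | 58–72 |
| Week 16 | 105–119 | 114–128 |
| Week 24 | 161–175 | 170–184 |

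The SAP limit is 6 × 7 = 42 days. That is before day 58, and below the 48-day minimum for SD in protocol 10.4. Only early or unscheduled scans could fail it. It is 119 days shorter than 161 and 126 days shorter than 168.

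**Direction.** Everyone who meets the 24-week rule meets the 6-week rule, so the SAP rate is never lower. This needs no assumption.

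**Size, under assumptions.** Neither document gives progression rates for cohort E. Assume that CR and PR count under both rules, that non-responders have exponential time to progression with median m of 2 to 9 months (30.44 days each), and that scans fall mid-window. SAP 5.1.2 runs SD duration to the progression date, so progression first seen at the Week 24 scan still gives at least 161 days. The comparison is therefore progression-free at the first scan (day 56 + 9 = 65) against progression-free at the Week 16 scan (day 112 + 9 = 121):

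DC = OR + (1 − OR) × exp(−ln 2 × t / m)

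At 20% OR and m = 2 months (60.88 days):

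- SAP rule: 0.20 + 0.80 × 0.477 = 58.2%
- 24-week rule: 0.20 + 0.80 × 0.252 = 40.2%
- Rise: 18.0 points

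At m = 9 months the rates are 87.9% and 78.9%, a rise of 9.0. Protocol 7.7 supplies the 20%, 60% and 80% response rates; 0% is added as the extreme. The share is the rise divided by the SAP rate, for example 18.0 / 58.2 = 31%.

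| OR rate | Rise in DC rate (points) | Patients of 20 | Share of duration-of-DC set with SD under 24 weeks |
|---|---|---|---|
| 0% | 11.2–22.5 | 2.2–4.5 | 13–47% |
| 20% | 9.0–18.0 | 1.8–3.6 | 10–31% |
| 60% | 4.5–9.0 | 0.9–1.8 | 5–11% |
| 80% | 2.2–4.5 | 0.4–0.9 | 2–5% |

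**Sensitivity** (points, at 0 / 20 / 60 / 80% OR):

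- Extremes of scan timing (day 58 v 128, day 72 v 114): 8–28 / 7–23 / 3–11 / 2–6.
- All events exactly dated (day 65 v 161): 18–32 / 15–25 / 7–13 / 4–6.
- SD required on the Week 24 scan itself (day 65 v 170): 20–34 / 16–27 / 8–13 / 4–7.

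**Choice of day limit.** On-schedule Week 16 scans end by day 128 and Week 24 scans start at day 170, so 161 and 168 days classify on-schedule scans identically. A simulation of 400,000 patients at 0% OR gave the same DC rates for limits of 161, 168 and 170 days.

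**The case against.** The NSCLC rule is written out separately for SD and for Non-CR/Non-PD and appears in two SAP sections, so it looks like a deliberate tumour-specific definition. On that view the only defect is the missing declaration. That the rule looks deliberate is fair, and it rules out a typing slip. It does not supply authority: no protocol amendment gives cohort E a 6-week rule. Nor does timing explain it. SAP version 2.0 (25 October 2021) predates protocol Amendment 8 (4 March 2022), but the log for that amendment does not touch this endpoint.

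A second objection is that 161 days is itself short of a literal 24 weeks (168 days), and that cohort E needs no window allowance because its Week 24 scans fall at day 170 or later. The arithmetic is right. But the protocol says cohort E follows cohort F, for which the SAP uses 161, and the choice matters only for off-schedule scans or for events on days 161 to 167.

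Three further points stand:

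- The Non-CR/Non-PD branch should not arise, since cohort E requires measurable disease.
- The 48-day minimum may still apply through the SAP's reference to protocol 10.4, though on-schedule scans pass either limit.
- The size depends heavily on assumptions, and only the direction is certain.

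The weight is also limited. DC is a descriptive secondary endpoint here, and PFS is still shown by Kaplan-Meier and per patient, so durability remains visible.

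**Conclusion.** The concern holds: the SAP is wrong as written for this endpoint. The mismatch, the absence of any declaration, and the fact that on-schedule scans always pass the 6-week limit rest on the documents alone. So does the direction of the effect.

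The size is an illustration that depends on exponential progression, the chosen medians and mid-window scans. At the 60% response rate the protocol calls clinically relevant, it is one or two patients in 20. At the 20% rate it uses for a false positive signal, it is about two to four. The main figures are the cautious reading; both alternative ways of dating or requiring 24 weeks give larger rises. The sample size and the primary endpoint do not change, so this should be corrected but does not threaten the trial's main conclusion.

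**What to change.** In SAP 5.1.2 and 5.2.2.2, apply the 24-week rule to cohort E with the same limit as the breast cohorts (Week 24, at least 161 days). In the same place, replace the reference to randomisation with first treatment administration including the run-in. The Non-CR/Non-PD branch may stay at the same limit, in line with protocol 7.3.1. Base duration of DC on the resulting set.

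If a 6-week rate is wanted for NSCLC, report it in addition under its own name, declare it in SAP 4.2, and reconcile it with the 48-day minimum in protocol 10.4.

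The cost is SAP wording and one derivation, with no new data. The reported cohort E DC rate will be the same or less favourable, and the duration-of-DC set the same size or smaller.
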